1.2. Objectives

Primary Objective:

- To validate biomarkers that are associated with severe RSV infection and respiratory sequelae.

Secondary Objective(s):

- To analyze dynamics of biomarkers in the upper and lower airways of children with RSV infection and compare these with blood
- To validate currently used case definitions and severity measures for RSV infection in infants

- To determine risk factors for severe RSV disease
- To determine long term sequelae of RSV infection in the first year of life

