1.3. Study design

This will be a monocenter, prospective, observational case-control study conducted across 2 consecutive years in the Wilhelmina Children's hospital and surrounding general practitioner (GP) offices and general hospitals. This case-control study will validate discovered biomarkers related to RSV infection susceptibility and disease severity in the RESCEU case-control study and birth cohort study. In addition, dynamics of the same biomarkers will be analysed in the upper and lower airways to better understand the sources of these biomarker signals. For this a validation cohort of previously healthy infants with different severities of RSV infection will be used and compared to healthy infants.

The following subgroups will be studied:

- Ventilated infants (n=40)
- Hospitalized, non-ventilated infants (n=40)
- Medically attended non-hospitalized infants (n=40)
- Healthy infants (n=40)

Children will be recruited during two RSV seasons. If RSV is suspected but not tested as part of routine care a point of care test for RSV will be done. Samples will be collected within 96 hours after hospitalization or start of symptoms in infants who are not admitted and repeated after 6-8 weeks (convalescence). Healthy infants will be recruited year round. Collection of samples of healthy controls will be done once. There will be annual follow up by questionnaire for up to 3 years.

Blood, stool, buccal, urine and nasopharyngeal samples will be obtained from all RSV positive infants at moment of infection and in convalescence 6-8 weeks later. In ventilated RSV positive infants, bronchoalveolar lavage (BAL) and/or tracheal aspirate samples will be obtained in combination with routine clinical care. Healthy infants will have blood, stool, buccal, urine and nasopharyngeal samples only at enrolment (i.e. there will be no follow up sampling).

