1.4. Study population

1.4.1. Population (base)

The total study population consists of 160 (previously) healthy infants (<1 year of age). 120 infants with RSV infection will be recruited, who are divided in the following groups:

- Ventilated infants (n=40)
- Hospitalized, non-ventilated infants (n=40)
- Medically attended non-hospitalized infants (n=40)

In addition a group of healthy infants (n=40) without infection at moment of sampling will be recruited to validate whether the discovered biomarkers would also be able to distinguish between infants with and without infection.

All infants will be recruited at the Wilhelmina Children's hospital and surrounding GP offices and general hospitals during 2 consecutive RSV seasons.

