4.1. Primary study parameter(s)

The primary endpoint is disease severity of RSV infection in the first year of life. The use of biomarkers that are associated with severe RSV infection and respiratory sequelae will be validated. RSV disease severity will be categorized in the following categories: hospitalized non-ventilated, hospitalized ventilated (PICU admitted) and non-hospitalized infants with RSV. If an infant was first recruited in the non-hospitalized group and is admitted during the course of RSV disease, the infant will be changed to the hospitalized non-ventilated or ventilated (PICU admission) group. In addition a control group of healthy controls will be used.

Large data sets are necessary for integrative computational analyses in order to identify profiles associated with disease severity. These data will come in a wide variety of formats depending on the sample being tested and the test being undertaken. In some cases analyses will be undertaken using standard techniques while others may require novel techniques. We will work closely together with other partners in the consortium.

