4.2. Secondary study parameter(s)

1. Values of biomarkers in the upper and lower airways of children with RSV infection and comparison with the values of these biomarkers in blood.

Values of biomarkers for (severe) RSV infection will be compared between upper and lower airways (in ventilated infants) and blood (all infants). Results will be compared within individual children and between children of different symptom severity categories (hospitalized non-ventilated, hospitalized ventilated and non-hospitalized infants with RSV infection).

2. Performance of currently used case definitions and severity measures for RSV infection in infants.

Clinical data about symptom severity of the participating infants will be compared with existing case definitions and severity measures. The performance of these case definitions and severity measures will be described as percentage agreement and percentage missed or incorrect diagnosis. In addition a new, simplified severity score (which will be developed within PROMISE and will be based on an extensive literature review and data obtained from the RESCEU infant studies) will be validated in this study.

3. Risk factors for severe RSV disease

Risk factors for severe RSV disease will be determined using demographic parameters, clinical parameters and outcome and laboratory test results of participating infants. Results will be displayed as categorical data with percentages or continuous variables with mean (+/-SD) and/or median (interquartile range). Comparisons between groups of different severity (hospitalized non-ventilated, hospitalized ventilated and non-hospitalized infants with RSV) and healthy controls will be performed using chi-square for categorical variables, Student-t-test for normally distributed continuous variables or Mann-Whitney U test for not normally distributed continuous variables. Multivariate regression analysis will be performed to analyse multiple risk factors for severe RSV disease.

4. Long-term sequelae of RSV infection in the first year of life

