Long-term sequelae (amongst others recurrent wheeze) will be determined using the yearly questionnaires. Results will be displayed as categorical data with percentages or continuous variables with mean (+/-SD) and/or median (interquartile range). Comparisons between groups of different severity (hospitalized non-ventilated, hospitalized ventilated and non-hospitalized infants with RSV) will be performed using chi-square for categorical variables, Student-t-test for normally distributed continuous variables or Mann-Whitney U test for not normally distributed continuous variables.

5. Ethical considerations

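### Risk factors for severe RSV disease are compared with healthy controls as well as across RSV severity groups, so a factor linked only to infection can be reported under severity

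*Protocol*

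**What the plan says.** The secondary objective in Protocol section 1.2 is "To determine risk factors for severe RSV disease". Section 4.2 item 3 serves it with demographic data, clinical parameters and outcome, and laboratory results. It plans that "Comparisons between groups of different severity (hospitalized non-ventilated, hospitalized ventilated and non-hospitalized infants with RSV) and healthy controls will be performed using chi-square", with a t-test or Mann-Whitney test for continuous variables. A multivariable regression for severe disease follows, and the infants who enter it are not named.

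Other sections treat the healthy group differently:
- Section 4.1: "RSV disease severity will be categorized in the following categories: hospitalized non-ventilated, hospitalized ventilated (PICU admitted) and non-hospitalized infants with RSV". All three categories are RSV-positive, and controls are mentioned afterwards as an addition.
- Section 1.4.1: healthy infants are recruited "to validate whether the discovered biomarkers would also be able to distinguish between infants with and without infection".
- Section 1.3 names two targets for the biomarkers: the study will "validate discovered biomarkers related to RSV infection susceptibility and disease severity".
- Section 4.2 item 4, on long-term sequelae, uses nearly the same sentence as item 3 but without controls: "Comparisons between groups of different severity (hospitalized non-ventilated, hospitalized ventilated and non-hospitalized infants with RSV) will be performed using chi-square for categorical variables".

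**The concern.** Two questions share one heading. The first is whether a factor differs by severity among infants who have RSV. The second is whether it differs between infants with medically attended RSV and infants without it. A comparison with healthy infants answers the second. It can be significant for anything tied to catching RSV or being brought to care for it, such as siblings, day care or season, even when the factor is equally common in ventilated, hospitalised and non-hospitalised infants.

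Item 3 is especially exposed because it also tests clinical and laboratory results. Many of these can be expected to differ between an acutely ill infant and a well one at any severity. Section 1.2 has no objective on risk factors for infection, so the control contrasts have no other risk-factor heading to be reported under. The mild RSV group makes it possible to isolate severity, and a risk-factor list that mixes both kinds of contrast loses that advantage.

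**Working it through.** **Inputs from the Protocol.** Three RSV groups of 40 and one healthy group of 40 (sections 1.3 and 1.4.1): 3 × 40 = 120 RSV-positive infants and 4 × 40 = 160 in all, as section 1.4.1 states. The Protocol gives no alpha, effect size or factor prevalence, so it has no figure of its own to reproduce here.

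**Assumptions.** Two-sided alpha 0.05, uncorrected chi-square. A binary factor has prevalence p0 in healthy infants and the same prevalence p1 in all three RSV groups, so there is no severity effect.

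**Formula.** For n = 40 against 40, with m = (p0 + p1)/2:

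power ≈ Φ{ [ |p1 − p0| − 1.96 √(2m(1−m)/n) ] / √( [p0(1−p0) + p1(1−p1)]/n ) }

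- p0 = 0.30, p1 = 0.50: m = 0.40; √(2 × 0.24/40) = 0.1095; √((0.21 + 0.25)/40) = 0.1072. (0.20 − 0.2147)/0.1072 = −0.137, so power ≈ 45%.
- p0 = 0.30, p1 = 0.60: m = 0.45; √(2 × 0.2475/40) = 0.1112; √((0.21 + 0.24)/40) = 0.1061. (0.30 − 0.2180)/0.1061 = 0.773, so power ≈ 78%.

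**Check.** The two pairwise columns come from exact binomial enumeration; the other two come from simulation (200,000 replicates).

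| Controls v every RSV group | Ventilated v healthy | Four-group test | Ventilated v non-hospitalised RSV | Three RSV groups |
|---|---|---|---|---|
| 40% v 55% | 29% | 25% | 6% | 5% |
| 30% v 50% | 46% | 43% | 6% | 6% |
| 30% v 60% | 80% | 81% | 5% | 5% |

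**Sensitivity to the assumed effect.** With 30% in controls and odds ratios for infection of 1.5, 2, 3 and 4, the formula gives 13%, 32%, 67% and 86% for ventilated versus healthy. With 50% in controls it gives 14%, 33%, 64% and 82%. Across these scenarios a single contrast among RSV groups, or the three-group test, stays at about 5% to 6%. (If all three pairwise RSV contrasts are run unadjusted, at least one is significant in about 11% to 14%.)

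**Who the controls are.** Section 2.2.1 takes them from infants in hospital for minor elective surgery, with orchidopexy and inguinal hernia repair among the examples, or for a check-up that needs blood. Section 1.3 recruits them all year and the RSV infants in season, although section 1.4.1 places all recruitment in RSV seasons. Sex, age or season could therefore differ from the RSV infants for reasons unrelated to RSV. Section 1.4.1 asks only that controls be free of infection when sampled.

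**The case against.** The strongest reply is that the objective does not condition on infection. Comparing severe cases with uninfected infants is an ordinary case-control contrast for the overall risk of severe RSV disease, that is, of being infected and then becoming severely ill. On that reading siblings are a genuine risk factor, and the percentages above are power. This stands in part: including controls is not wrong in itself, and a reader who inferred a greatly inflated type I error would go beyond the document. But the overall-risk reading needs controls who represent the population that gave rise to the cases, and an elective-surgery or check-up sample recruited year round is not a clean version of that. Nor does it rescue the clinical and laboratory values that reflect acute illness.

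Two further replies hold as far as they go. The Protocol nowhere says that a difference from controls alone makes a severity factor, and the same sentence plans contrasts among the RSV groups, where an infection-only factor should show no gradient. It also never merges healthy infants with non-hospitalised RSV infants as one reference group, so no such model should be read into it.

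A reader might extend the point to the biomarker validation, because section 1.3 says "For this a validation cohort of previously healthy infants with different severities of RSV infection will be used and compared to healthy infants". The text does not support that: sections 1.3, 1.4.1 and 4.1 already keep infection and severity apart for biomarkers.

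Finally, these details could sit in an analysis plan that is not shown. Which infants enter the regression may well be settled there. The inclusion of controls in item 3, however, is stated in the Protocol and does not fit its heading.

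**Conclusion.** The point holds as a possible misreporting in one secondary analysis. Item 3 places healthy controls in the tests for severity factors, does not separate the two questions, and leaves open whether controls enter the regression. An infection-only factor can therefore be listed as a risk factor for severe disease; the Protocol does not say that it will be. In the illustration, ventilated versus healthy is significant in about 45% to 80% of studies when prevalence is 30% in controls and 50% to 60% in every RSV group, against about 5% for a contrast among RSV groups. Those figures rest entirely on assumed prevalences and alpha; a weak infection effect (odds ratio 1.5) gives only 13% to 14%. It should be corrected, because the change is small and removes a real ambiguity.

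**What to change.** In Protocol section 4.2 item 3, state that:

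1. Risk factors for severe disease are judged, univariably and in the multivariable regression, among the 120 RSV-positive infants, with non-hospitalised RSV infants as the reference.
2. Comparisons with the 40 healthy infants are reported in a separate table as descriptive or infection-related, with no severity claim.

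The biomarker text in sections 1.3 and 4.1 needs no change.

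The cost is a few sentences, with no new data or infants. There are two small downsides. The 40 controls leave the severity model, so a factor that acts only through infection appears in the second table. And the severity result is conditional on medically attended RSV infection, which can itself distort associations for factors that affect infection or care-seeking, so the report should state that condition.

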- Synthetic absorption matrix [SAM] 2 nasal strips
- Nasopharyngeal bacterial swab

- Venous or capillary blood sample (maximum of ~0.8ml/kg)
- Urine sample (clean catch or from gauze in a nappy)
- Stool sample (from a “dirty” nappy)
- Buccal swab

Questionnaires

Baseline

- At inclusion a questionnaire about pregnancy, perinatal course and potential risk factors for RSV-hospitalization and sequelae will be filled in

One year of age

- Assessment of respiratory symptoms by parental questionnaire at age 1 year through telephone contact/email/online
- Cost, resource use and Health-Related Quality of Life (HRQoL) data will be collected using questionnaires for caregivers

Two years of age

- Assessment of respiratory symptoms by parental questionnaire at age 2 years through telephone contact/email/online
- Cost, resource use and HRQoL data will be collected using questionnaires for caregivers

Three years of age

- Assessment of respiratory symptoms by parental questionnaire at age 3 years through telephone contact/email/online
- Cost, resource use and HRQoL data will be collected using questionnaires for caregivers

Handling and storage of samples

See table 1 for volume and frequency of sampling. Samples will be stored at the biobank of the UMCU. During the study, samples will be shipped to other laboratories for analysis. Some samples will be sent to laboratories in countries within the European Union (EU) and some samples may be sent to laboratories in countries outside the EU for analysis.

- Sample handling and processing
- Serum: Blood will be drawn into serum collection tubes containing a clot activator and refrigerated between 2°C - 8°C for a maximum of 24 hours. Tubes will be centrifuged at 3000 rpm, 4°C for 10 minutes, serum extracted and stored at -80°C for later analysis.
- Whole blood: Whole blood will be collected in Natrium Heparin tubes and have appropriate buffers added and then be spun down and stored at -80C for later analysis.
- Functional Genomics: Whole blood will be added to Paxgene tubes containing a RNA stabilization reagent and stored at -80°C. Subsequently, RNA will be extracted and gene transcription determined using next generation sequencing approaches.

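### The sequelae comparison omits the healthy controls, and the primary endpoint covers severity only, so the secondary sequelae objective is partly addressed and the sequelae part of the primary objective has no outcome

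*Protocol*

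**What the plan says.** **Objectives.** Section 1.2 gives the primary objective as "To validate biomarkers that are associated with severe RSV infection and respiratory sequelae". One secondary objective is "To determine long term sequelae of RSV infection in the first year of life".

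**Primary endpoint.** Section 4.1 states "The primary endpoint is disease severity of RSV infection in the first year of life", followed by "The use of biomarkers that are associated with severe RSV infection and respiratory sequelae will be validated". Section 2.1.1 has the same two sentences. The categories then listed in 4.1 are the three RSV severity groups, plus a healthy control group.

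**Sequelae analysis.** Section 4.2 item 4 takes sequelae, with recurrent wheeze as the example, from the yearly questionnaires. It then says "Comparisons between groups of different severity (hospitalized non-ventilated, hospitalized ventilated and non-hospitalized infants with RSV) will be performed using chi-square", with a t-test or Mann-Whitney test for continuous variables. No regression is mentioned.

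**Risk-factor analysis.** The matching sentence in item 3 reads "non-hospitalized infants with RSV) and healthy controls will be performed using chi-square for categorical variables". Item 3 also announces a multivariate regression, for severity only.

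**Follow-up.** Section 2.2.1 plans "Assessment of respiratory symptoms by parental questionnaire at age 1 year", and again at ages 2 and 3. Section 1.3 says "There will be annual follow up by questionnaire for up to 3 years", whereas the Summary says yearly up to the age of 3. Enrolment is at any age under 12 months (section 1.4.2).

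**The concern.** Long-term sequelae of an infection are an excess over what would be seen without it. A comparison confined to infected infants has no such reference. If wheeze were raised equally in all three severity groups, item 4 would show no difference and the excess would go unseen.

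The primary objective has two parts, severity and sequelae, but the primary endpoint is defined for the first only. An analysis plan that follows section 4.1 would have no outcome against which to validate a sequelae biomarker.

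The item 4 tests also take no account of age. Section 1.1 says younger infants are at greater risk of severe disease. Severity groups may therefore differ in age at infection, and so in the time between infection and a questionnaire set at a fixed age.

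**Working it through.** **1. Groups compared.** Items 3 and 4 of section 4.2 use nearly the same sentence and the same tests. Item 3 names three RSV groups and the healthy controls; item 4 names the three RSV groups only. Planned numbers: 3 × 40 = 120 RSV infants + 40 healthy = 160, which agrees with section 1.4.1. Item 4 therefore uses 120 of the 160.

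**2. Do controls have follow-up data?** The Summary limits the diary to RSV-positive children but puts no such limit on the yearly questionnaire. Section 2.2.1 labels the one-week contact as for healthy infants and the convalescent visit as for RSV-positive infants, but gives the age 1, 2 and 3 questionnaires no label. Section 1.3 rules out only follow-up sampling for healthy infants. Control questionnaires thus appear to be planned, though no sentence says so outright.

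**3. Objective against endpoint.** Section 1.2 covers severity and sequelae. The endpoint in sections 2.1.1 and 4.1 is severity. Section 4.1 repeats the intention to validate sequelae biomarkers but attaches no sequelae outcome. Section 4.2 item 4 has a sequelae outcome but no biomarker. No section pairs the two.

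**4. Time since infection.** Time = questionnaire age − age at infection. With infection at 0 to 12 months, this is 0–12 months at age 1, 12–24 at age 2 and 24–36 at age 3. The protocol gives no group ages, wheeze rates or recall window, so what follows rests on assumptions: mean age at infection 2 months (ventilated) v 6 months (non-hospitalized), the same wheeze rate in both groups, and wheeze counted from infection. Formula: P(at least one episode) = 1 − exp(−rate × t).

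| Rate per child-year | Age 1 (t = 10 v 6 months) | Gap, points | Age 3 (t = 34 v 30 months) | Gap, points |
|---|---|---|---|---|
| 0.3 | 22.1% v 13.9% | 8.2 | 57.3% v 52.8% | 4.5 |
| 0.5 | 34.1% v 22.1% | 12.0 | 75.7% v 71.3% | 4.4 |
| 1.0 | 56.5% v 39.3% | 17.2 | 94.1% v 91.8% | 2.3 |

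With a 30% risk per 12 months and the same ages, the figures are 25.7% v 16.3% at age 1, 48.0% v 41.4% at age 2 and 63.6% v 59.0% at age 3. With 40 per group and a two-sided 5% test, the chance of falsely finding more wheeze in the ventilated group is about 17%, 8% and 6%, against a nominal 2.5% in that direction. Equal mean ages give no gap.

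**5. What the added comparison could detect.** The protocol gives no sequelae rates, so these are assumed. Two-sided 5%, normal approximation, no dropout: power = Φ[(|p1 − p2| − 1.96·se0)/se1], with se0 pooled and se1 unpooled. Example, 40 controls at 20% v 120 RSV infants at 40%:
- pooled proportion = (8 + 48)/160 = 0.35
- se0 = √(0.35 × 0.65 × (1/40 + 1/120)) = 0.0871
- se1 = √(0.16/40 + 0.24/120) = 0.0775
- power = Φ[(0.20 − 0.1707)/0.0775] = Φ(0.38) = 0.65

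| Controls v RSV | 40 v 120 | 40 v 40 |
|---|---|---|
| 10% v 30% | 0.76 | 0.61 |
| 15% v 30% | 0.46 | 0.36 |
| 20% v 40% | 0.65 | 0.50 |
| 20% v 50% | 0.94 | 0.82 |

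From 20% in controls, 80% power needs about 44% (40 v 120) or 49.5% (40 v 40).

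**6. Follow-up length.** For an infant enrolled at 11 months, three years from enrolment is 36 months; follow-up to age 3 is 36 − 11 = 25 months.

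**The case against.** - **The controls had another purpose.** Section 1.4.1 recruits them to test whether biomarkers separate infants with and without infection. They are defined only as free of infection at sampling, nothing excludes earlier RSV, and they come from elective surgery or check-ups, year round. This stands: they are an imperfect reference. It does not explain why item 3 uses them and item 4 does not.
- **Modelling detail belongs in an analysis plan.** True, and that plan is not shown. But the objective and the endpoint are fixed in the protocol, and they do not match there.
- **A reader might infer that neither sequelae objective is answered, or that half the primary objective has no analysis at all.** The text does not support that. Item 4 answers whether sequelae differ by severity, and section 4.1 states an intention on sequelae biomarkers.
- **A reader might infer that control data are certainly collected and then discarded.** No sentence confirms that controls receive the questionnaires, and the descriptive part of item 4 is not limited to RSV infants.
- **A reader might infer that the severity contrast is biased by 8 to 17 points.** Those gaps depend on assumed ages and rates, on counting from infection, and on the age-1 questionnaire. They also concern at least one episode, whereas item 4 names recurrent wheeze. A past-12-months question would give every child the same recall length, and at ages 2 and 3 that window lies wholly after infection. Asking at fixed ages also has a merit: it compares children of the same age.

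**Conclusion.** Two points hold on the text alone. Item 4 omits the controls that item 3 includes, so the secondary sequelae objective is only partly addressed. The primary endpoint is severity alone, so the sequelae part of the primary objective has no matching outcome. Neither depends on an assumed number.

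The lack of adjustment in item 4 is a lesser point. Unequal time after infection is a reasonable inference from sections 1.1, 1.4.2 and 2.2.1, but its size cannot be derived from the protocol. Under the assumptions shown it could matter at age 1 and falls to about 2 to 5 points at age 3. It supports adjusting for age; it does not show that the planned contrast is biased by a known amount.

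The two statements of follow-up length are a minor inconsistency, since the Summary and section 2.2.1 agree on age 3.

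**What to change.** - **Section 4.2 item 4:** add the healthy controls as a comparison group. Add a regression adjusted for age at enrolment and the risk factors from the baseline questionnaire.
- **Section 2.2.1:** state that healthy controls receive the age 1, 2 and 3 questionnaires. Settle this before follow-up begins, because missed early data cannot be recovered.
- **Section 4.1:** name recurrent wheeze from the age-2 and age-3 questionnaires as the outcome for the sequelae biomarkers in the 120 RSV infants. Alternatively, take respiratory sequelae out of the primary objective.
- **Section 1.3 and Summary:** use one statement of follow-up length.

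**Cost.** These are text changes using data that appear to be planned already. If controls were not meant to receive the questionnaires, there is the added work of following 40 families. Because controls may have had RSV before or after enrolment and come from selected hospital visits, their RSV history should be recorded and reported as a limitation. With 40 controls only large differences are detectable, so the comparison should be reported as an estimate with its confidence interval.
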